### 3. Method

#### 3.1 Recruitment

##### 3.1.1 Initial Contact

Older adult participants will be recruited through the PREVENT-AD cohort as an optional sub-study, by reaching out to potentially eligible participants by phone and email. Screening procedures will involve verbally screening potential participants over the phone. A staff member doing the screening will begin with an overview of the HABS project. The screener will then obtain verbal consent (see telephone script). The telephone script will ask questions concerning inclusion and exclusion criteria. The total time to administer all screening questions is approximately 40 minutes. The telephone screen will also assess the level of physical activity via self-reported physical activity. If eligibility is verified, a date and time will be scheduled for a virtual meeting between the participant and a researcher where the formal study consent will be signed. Those individuals that are deemed ineligible from the screening call will have their forms kept in a separate file on REDCap. This information will be used to quantify how many were ineligible from the screening call and the reasons for ineligibility.

The criteria will be assessed by one of the listed study personnel. No special expertise is required to evaluate screening responses. If a participant requires exclusion due to information received during a session, they will be contacted via telephone or email and informed that they have been excluded from further study, nevertheless remaining part of the PREVENT-AD cohort. The reason provided for their exclusion will be brief and will include a statement such as, "Based on the data collected in your last session, we will not require any further testing. As indicated in the beginning, participation depends on several factors and not all participants qualify for the entire study."

##### 3.1.2 Consent Process for Participants

Participants' consent will be obtained remotely before they begin participating in research activities. The consent process will be administered by experimenters (i.e., research personnel described above). Individuals who agree to participate after the phone screen will receive a copy of the consent document in advance by email and will schedule a time to speak with an experimenter via videoconference. They will be asked to read, but not sign, the consent document before the phone call, and the experimenter will coordinate with the participant so they have enough time to read the document before the call. During the call, the experimenter will explain the study and answer any questions the participant has. If the participant wants to take part in the study, they will then sign the consent document electronically in the REDCap platform; this format is secure and easy for participants to use. The informed consent process will be completed while a researcher is videoconferencing with the participant and can answer any questions they may have. Participants will be made aware that their participation is completely voluntary, and they may quit the experiment at any time.

Participants in the intervention arm will be invited to participate in a social motivation manipulation involving a younger study partner. The intervention group will be asked to invite an interested younger child/grandchild 18 years and older but younger than 40 to join them at the time of consent. The social motivation intervention represents the younger generation family member dyad. The study partner will sign as well informed consent during session T0, follow the same timeline as their older relative, receiving feedback on their relative's accelerometer data. Study partners have a streamlined intervention whereby they do not undergo accelerometry testing and only have two videoconferenced sessions and one phone session. Study partners partake in the 4 weeks of daily messages and receive feedback on their relative's performance. The study partner will complete an overlapping, but briefer battery of pre and post compared to their older adult family members. Study partners will not undergo a remote physical assessment evaluation and will not be required to have physical or virtual contact with their older adult family members other than their regular interactions.

### 3.1.3 Consent process for minors aged 14 up to before 18 years old.

Younger study partners between the ages of 14 and up before their 18th birthday, will be required to provide remote written assent for their participation in the study by using a unique consent form and the remote written consent of their parent or legal guardian. This special group of intrafamilial study partners will be the grandchildren of the main participant younger than 18 years old. Older participants in the intervention group who do not have grandchildren will be assigned an extrafamilial study partner aged 18 years or older. Written assent from the minor participant and the written consent of their parent or legal guardian will be obtained during session T0. Contact will be through the main study participant who will provide the contact details for their younger study partner (grandchild or child). These study partners will follow the same timeline as their older relatives, receiving feedback on their relative's accelerometer data. Study partners have a streamlined intervention whereby they do not undergo accelerometry testing and only have two videoconferenced sessions and one phone session. Study partners partake in the 4 weeks of daily messages and receive feedback on their relative's performance. The study partner will complete an overlapping, but briefer battery of pre and post compared to their older adult family members. Study partners will not undergo a remote physical assessment evaluation and will not be required to have physical or virtual contact with their older adult family members other than their regular interactions.

\*\*The study will recruit up to 120 younger study partners including individuals between 18-40 years old and between 14 and up to 18 years old.

### **3.3 Exclusion Criteria**

- Current or previous formal diagnosis of a DSM-V Axis I or II disorder including Major Depression (not including postpartum depression or anxiety)
- History of major psychiatric illness including schizophrenia
- Current treatment for cancer – except non-melanoma skin cancer
- Neurological condition (MS, Parkinson's, Dementia, Stroke) or moderate to severe traumatic brain injury.
- Current alcohol or substance abuse
- Current treatment for congestive heart failure, angina, uncontrolled arrhythmia, DVT or other cardiovascular condition
- Myocardial infarction, coronary artery bypass grafting, angioplasty or other cardiac event in the six months before enrollment.
- Regular use of an assisted walking device or significant increase in pain when walking
- Use of any antipsychotic, anti-depressant, anti-anxiety, and ADD/ADHD medications, other than for sleep.
- Not fluent in English or French
- No regular access to a smartphone or computer with internet
- Involvement in conflicting research studies currently or recently

### **3.4. Participants ineligible due to physical activity criteria**

Participants who do not want to increase their physical activity levels and are thus ineligible for the main study would have the option to join the study for the first 3 sessions up to before the 4-week intervention. This would allow for the acquisition of behavioural measures up to yellow visits in ineligible participants. The objective would be to understand physical activity as it relates to Alzheimer's disease risk and its related motivational factors. This piece of the study would follow the same parameters, cognitive measures, and questionnaires as the one collected for the main study for the first three sessions up to before the intervention window. Compensation would be provided accordingly.

### **3.5 Study Partner inclusion criteria**

- Can be identified as child or grandchild of participant (biological or adopted), 14 years or older.
- Can be a young adult (18 years or older) who is not a relative of the main participant, in case a grandchild or child is not available.
- Stable on psychoactive medications for more than 6 months.

- In contact with the primary participant more than once per 12 months at baseline
- Lives anywhere accessible by mail in Canada if 18 years and older, or anywhere accessible by mail in Quebec if 14 years and older but younger than 18 years.
- Adequate vision to complete the cognitive tasks
- Able to speak, read, and write English or French
- No diagnosis of neurological disease or unstable health condition
- Regular access to a computer with internet or a smartphone

### 3.6 Study Partner exclusion criteria

- Not in contact with the primary participant more than once per 12 months at baseline

### 3.7 Extrafamilial study partners

Young adults (aged 18 to 40) will be recruited from the community to participate as extrafamilial study partners. These participants will be paired with an older adult participant who does not have a child or grandchild that can participate but is otherwise eligible. Young adults will be recruited through flyers posted around the McGill University campus as well as an advertisement posted on the Department of Psychology's SONA participant pool. Participants will receive either 2 SONA credits or \$40 CAD for their participation. The study timeline for extrafamilial study partners will consist of one additional, remote visit approximately one week after the formal consent form is signed. This visit will consist of a 1 hour Zoom call with the older adult participant, the extrafamilial study partner, and a member of the research team.

The purpose of this visit will be to introduce the older adult to the younger study partner and provide the participants with an opportunity to get to know one another. This conversation will allow the extrafamilial study partner to create the personalized messages ("kudos") for the social messaging application. The younger study partner will be asked to lead the conversation and will be provided with a list of questions that they can ask in order to get to know the older adult. After the conversation, the older adult will be asked to log off the Zoom call and the younger study partner will be asked to provide the 30 personalized messages.

### 3.8. Financial compensation

Financial compensation will be offered as follows:

#### 3.8.1. Intervention Group

##### Participant

Remote Meeting	Pay
Session 1	\$20
Session 2	\$20
Session 3	\$20
Session 4	\$20
Accelerometry Completion	\$20
TOTALS	\$100 for all sessions and device returned

**Study partner**

REMOTE Session	Pay
TOTALS	\$40 for study completion

**3.8.2. Control Group**

Remote Meeting	Pay
Session 1	\$20
Session 2	\$20
Session 3	\$20
Session 4	\$20
Accelerometry Completion	\$20
TOTALS	\$100 for all sessions and device returned

**3.8.3 Cross-over segment**
**3.8.3.a Crossed to Intervention Group**
**Participant**

Remote Meeting	Pay
Session 1	\$20
Session 2	\$20
Session 3	\$20
Session 4	\$20
Accelerometry Completion	\$20
TOTALS	\$100 for all sessions and device returned

**Study partner**

REMOTE Session	Pay
TOTALS	\$40 for study completion

**3.8.3.b Crossed to Control Group**

Remote Meeting	Pay
Session 1	\$20
Session 2	\$20
Session 3	\$20
Session 4	\$20
Accelerometry Completion	\$20
TOTALS	\$100 for all sessions and device returned

**3.8.3.c Donation to the Alzheimer's Society**

Based on the participant's physical activity performance and their pre-set goals (# of steps increase or amount of time increase being active) during the 4-week intervention period, a maximum amount of 3.00\$ per week would be saved to be donated to the Alzheimer's society at the end of the intervention (up to 18.00\$ for the whole intervention).

Week	Donation
Week 1	Up to 3.00\$
Week 2	Up to 3.00\$
Week 3	Up to 3.00\$
Week 4	Up to 3.00\$
Total Amount	Up to 12\$

The 3.00\$ will be saved for donation if the participant achieves 100% of their goal on a given week.

### 3.8.3.d Donation to the Alzheimer's Society of Montréal for the cross-over segment

The donation to the Alzheimer's Society of Montréal will follow the same principle than for the first segment of the study for those participants who cross into the intervention:

Week	Donation
Week 1	Up to 3.00\$
Week 2	Up to 3.00\$
Week 3	Up to 3.00\$
Week 4	Up to 3.00\$
Total Amount	Up to 12\$

The 3.00\$ will be saved for donation if the participant achieves 100% of their goal in a given week.

## 4. Methods/Assessments

### 4.1 Overview

In 120 sedentary and cognitively asymptomatic older adults (60 years and older) we will test whether a behavioural intervention combining social motivation, and self-transcendence messages decreases the amount of time participants are sedentary, as measured by accelerometry. We will use a stratified randomization scheme to ensure that half of the participants in each group will be randomized and stratified by their risk of developing Alzheimer's disease: to the social motivation + self-transcendence messaging (intervention) and the other half will be randomized to a daily activity monitoring group (active control). Participants will not be explicitly told to exercise as part of the study, but during the experiment they will receive messages that encourage walking or decreasing sedentary time. The primary measure of interest is decrease in sedentary behavior. All participants will be recruited from the PREVENT-AD cohort (STOP-AD Centre) at the Douglas Mental Health University Centre. Participants will be screened remotely by researchers affiliated with McGill University under the direction of [name].

### 4.2. Study design

The HABS study is a remote behavioural intervention that is conducted as a single-blinded randomized controlled trial. Recruited participants will be categorized as either high or low risk for Alzheimer's disease, in accordance with Aim 1 to determine the extent to which the behavioral intervention improves physical activity in at-risk older adults. Participant classification into high and low risk is based on their already known biomarker and cognitive status available from PREVENT-AD using a multimodal risk score. Note, that this does not involve collection of any new data and this data is not shared with participants as per the PREVENT-AD protocol. For participant classification into high risk, an individual's score is taken from a two-tier system of variables. The first tier involves variables where a positive result involves higher risk for Alzheimer's disease: Amyloid Tau Index (ATI)  $\leq 1$ , and p-tau in cerebrospinal fluid,  $\beta$ -Amyloid, and Total tau in PET, or APOE  $\epsilon 4/\epsilon 4$  or  $\epsilon 4/\epsilon 3$  status. A single positive value in any of these variables classifies the participant into the higher risk group. The second tier involves variables that independently are not sufficient for higher risk classification but together with a second variable might indicate higher risk: Overall cognitive performance (i.e., Repeatable Battery for the Assessment of Neuropsychological Status [RBANS]), episodic memory (i.e., Rey Auditory Verbal Learning Test [RAVLT]), hippocampal volume on MRI, APOE  $\epsilon 4/\epsilon 2$  status, Framingham Risk Score, and history of depression or consumption of psychotropic medication. Any combination of two variables from this tier classifies the participant into the higher risk group. Participants that are not classified into the higher risk group either because they had negative results to all risk variables or because they had a positive score to only one risk variable from the second tier, will be randomized into the low-risk group. We expect that approximately 50% of our participants will be in the high-risk group. We are using stratified randomization to ensure that each higher risk participant will be equally distributed across the intervention and control groups. The participants in each risk group are randomized to either a social motivation group (intervention) or control with a ratio of 1:1. The stratified randomization scheme is prepared by the Harvard Catalyst Biostatistical Group using a permuted block method with random blocks [16]. The randomization scheme will be uploaded in the REDCap randomization module. At the end of the first study period, participants will be offered to participate in a follow-up to ascertain maintenance which will consist of a cross-over into the alternative arm to which they initially were randomized. The study consists of two 4-week study periods with at least a 6-week washout period in between. This trial is registered on clinicaltrials.gov with an identifier NCT04315363. This study received ethical approval from Northeastern University Institutional Review Board (IRB).

**NOTE ON STUDY DESIGN AND SINGLE-BLINDING:** It is important to note that in order maintain the single-blind nature of the study, participants will not be specifically told that the daily messages are the study intervention. Therefore, the consent form will simply mention that some participants may receive motivational messages, but will not elaborate further.

Hence, in terms of the cross-over design, it will be described as a long-term follow up in the ICF in order to maintain the single-blind and not bias the participants. A debriefing session will be held at the end of period 1 to explain to the participants that the motivational messages were the intervention and they will be offered to cross-over into the opposite arm. See section 5.6 for more information regarding the cross-over.

#### PERSONNEL:

All staff and personnel associated with screening, collecting data, and analyzing data will have been trained and will have undergone all necessary research modules for safety and research ethics. [name] will meet with all staff on a regular basis to ensure that they are conducting research protocols appropriately. In addition, all staff who interact with participants are certified in Automatic External Defibrillator (AED) and CardioPulmonary Resuscitation (CPR). All staff who administer remote study sessions will be familiar with an emergency protocol (including calling emergency services) to prepare for the unlikely event that a participant has a medical emergency during a video or phone appointment.

[figure not shown]
### RESEARCH ACTIVITIES:

After obtaining informed consent, participants will complete screening measures for anxiety, depression, and cognitive impairment. If they pass these screenings, they will be randomized into the intervention (social motivation + self-transcendence messaging or control group). After randomization, participants complete a baseline non-exercise cardiorespiratory fitness (CRF) estimation (using heart rate measurement), short virtual physical assessments involving walking and sitting-to-standing, and neuropsychological and behavioural assessment during the 'Consent Session' and at 'Time 1' (Figure 1).

## 5 Intervention

### 5.1 Study timeline

An illustration of the study timeline can be seen in Figure 1. Informed consent is obtained at the initial video-conferenced meeting. Each participant undergoes a baseline session (T1) one week before the beginning of the intervention. As a baseline, participants wear a wrist-worn accelerometer on their non-dominant hand to assess physical activity (see physical activity monitoring). Physical assessments will be administered at baseline. The accelerometer is worn for a week. The intervention lasts 4 weeks, during which participants receive daily intervention messages via email or phone. Participants are fitted with the accelerometers again for a one-week mid-intervention period. The post-intervention session (T3) is scheduled at the beginning of the last intervention week (week 4), during which participants repeat psychosocial surveys and neuropsychological tests. All sessions are administered remotely through online surveys and computer tasks (please see timeline document).

### 5.3 Daily messaging

[figure not shown]
The 4-week intervention consists of daily self-transcendence messages via email using the encrypted online software oTree, an open-source platform for implementing messaging surveys, which allows for accessibility via desktop or smartphone [17]. Unique, coded links are assigned to each participant at enrollment. Participants will be requested to: "For the next 30 seconds contemplate the warm feelings you have towards a loved one as vividly as you can. Think about a situation where the following wish comes true for your loved one: May you be well". Examples of daily self-transcendence prompts rotate among:

- May you be well
- May you be happy
- May you be safe
- May you be at ease
- May you be healthy

- May you be peaceful
- May you find wholeness
- May you be joyful

Each day if they reach their physical activity goal, the main participants will receive messages from a pre-set list of messages composed at the consent session by their study partners (see Annex A – time capsule). The participant will then rate their mood and confidence in implementing the health tips, the goal of which is to examine the changing in well-being and self-efficacy of physical activity throughout the intervention. During weeks 2 and 4, they also receive daily reminders to continue wearing their accelerometer. This daily message survey setup is displayed in Figure 2. The researcher's contact information is displayed on each survey page to enhance compliance. Participants' responses are tracked and those that do not complete the survey by a specified time of day are contacted the following day by research assistants to prevent technical failures.

In addition to self-transcendence health messages, participants in the intervention arm will receive feedback about their daily physical activity using the CentrePoint encrypted software package from Actigraph (<https://actigraphcorp.com/cdh/>). The CentrePoint data hub is a home-based communication gateway that securely transmits data captured by the Actigraph activity monitors to provide near real-time feedback to participants about daily physical activity.

**Figure 2.** Messaging system setup and logic. Each participant (represented by  $P_x$ , where  $x$  designates the participant number) receives their unique link. In that link, they follow a series of pages each day that contain their unique questions and parameters based on the inputted comma-separated values (CSV) file. The system does not initiate until the participant begins on their first day and then repeats for 28 days (4 weeks) for the duration of the daily messaging intervention. The process occurs synchronously for all other participants. Links that are not activated simply remain idle until a participant is assigned that link

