Participants will be assessed remotely with accelerometers and have their cardiorespiratory status estimated. The estimation uses a regression equation that includes age, sex, body mass index, and resting heart rate. We will obtain a non-exercise CRF estimation before and after the four-week intervention. To perform the CRF estimation, which will be remote, we will ask participants to report their supine resting heart rate after they have rested quietly for ten minutes. Participants will also complete a remote physical assessment focused on their basic walking speed, their ability to transition repeatedly from sitting to standing, and their balance.

Accelerometers, chargers, and related materials will be sent to participants through the mail after the consent meeting and will be returned after the end of the first study period. Accelerometry data will be recorded during wakefulness and sleep, with the exception of bathing or swimming, for the week between T1 and T2 (before the intervention begins; i.e., baseline), for two separate weeks during the 4-week intervention (with additional days during this timeframe for any participant who does not wear the devices consistently during the original period). This will characterize changes in physical activity from baseline and maintenance. It will be assessed using two accelerometers worn simultaneously. The first is a wrist-worn tri-axial accelerometer (ActiGraph GT3X Link, Pensacola, FL). This accelerometry data will be downloaded in 60-second epochs (ActiLife software, ActiGraph, Pensacola, FL) and will be screened for wear time using standard methods [26]. The second device is a tri-axial accelerometer and inclinometer and will be worn on the thigh using an adhesive.

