#### 6b Data analysis

Outcome measures outside of the neuropsychological assessment battery are as follows:

Outcome measure	Type	Timeframe	Brief description
Total step count (average steps/day)	Primary	Week 0 (baseline); Week 2; Week 4.	This metric quantifies the change in the average number of steps taken each day, from the baseline, Week 2, and Week 4. It is a marker of change in habitual ambulatory activity.
Sedentary behavior (average min/day)	Primary	Week 0 (baseline); Week 2; Week 4.	This metric quantifies the change in the average amount of time spent sedentary each day, from the baseline, Week 2, and Week 4.

			2, and Week 4. It is a marker of time spent inactive.
Moderate-vigorous activity (average min/day)	Secondary	Week 0 (baseline); Week 2; Week 4.	This metric quantifies the change in the average amount of time spent engaged in moderate-to-vigorous physical activity each day, from the baseline, Week 2, and Week 4. It is a marker of physical activity.
Walking Cadence	Secondary	Week 0 (baseline); Week 2; Week 4	This metric reflects the participant's average steps per minute. We will examine change from baseline over the course of the intervention.
Walking Bouts	Secondary	Week 0 (baseline); Week 2; Week 4	This measures the number of 'bouts' of physical activity (in our case, steps). We will have two counts: the number of 5+ minute bouts and the number of 10+ minute bouts of walking. We will examine changes from baseline over the course of the intervention.

A spreadsheet holding the list of neuropsychological assessments to be used, with brief descriptions, is attached. They will be administered at T1 (Week 0), T2 (Week 1), and T3 (Week 4).

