To test our main hypothesis that social motivation + self-transcendence messaging + home-based physical training will produce the largest increase in physical activity over the course of the 4-week intervention compared to the active control, we will perform repeated measures ANCOVAs (with group as a between-subject factor and pre-post session as a within-subject factor). This hypothesis will be examined by analyzing total number of steps and percent time sedentary. We will analyze structural/functional MRI connectivity to test the hypothesis that increased physical activity following the intervention is associated with enhanced brain connectivity between brain regions in reward valuation (i.e., ventral tegmental area and ventral striatum) and social processing (vmPFC). We will conduct seed-based functional connectivity analyses using methods as in our prior research [9, 29-31]. To mitigate the influence of motion, we will identify and address artifactual motion outliers in data modeling, and employ quality assurance software to mitigate head motion artifacts and physiological aliasing ([https://www.nitrc.org/projects/artifact\\_detect](https://www.nitrc.org/projects/artifact_detect)). We will control for the effects of demographic variables (e.g., age, sex, education, diet, mood, socioeconomic status, alcohol, vascular risk factors and sleep). We apply a whole-brain height threshold of  $p < 0.001$  ( $T = 3.24$ ) and false discovery rate cluster threshold of  $p < 0.05$ . We will examine brain modularity, which indexes the segregation between networks, and has previously been shown to predict cognitive gains after a physical exercise intervention [20]. In addition to these hypothesis-driven analyses, we will perform an agnostic, data driven multi-voxel pattern analysis of resting-state data using an approach published by our collaborator [21].

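### The step-count primary outcome has no wear-time denominator, while the intervention arm has added reasons to wear the device, so a difference in wear could appear as a step effect

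*Protocol*

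**What the plan says.** **Outcomes.** The table in protocol section 6b lists two accelerometer primary outcomes, "Total step count (average steps/day") and "Sedentary behavior (average min/day"), each as change from a baseline week to weeks 2 and 4. On steps it adds: "This metric quantifies the change in the average number of steps taken each day". The analysis text of the same section treats the sedentary outcome differently: "This hypothesis will be examined by analyzing total number of steps and percent time sedentary". The mixed-model paragraph also uses a percentage for sitting and lying time, but keeps a plain count of steps.

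**Wear handling.** Section 5.5 says that the wrist data "will be screened for wear time using standard methods". It also allows extra days for participants who wear the devices inconsistently, asks for round-the-clock wear except when swimming or bathing, and adds a thigh-worn device. No minimum hours, minimum days or wear adjustment is stated. The SAP covariates are age, sex, socioeconomic status, neighbourhood walkability and the Alzheimer's risk score.

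**Reminders.** Section 5.3 states: "During weeks 2 and 4, they also receive daily reminders to continue wearing their accelerometer". These belong to the messaging system, of which the Figure 2 caption says: "The system does not initiate until the participant begins on their first day and then repeats for 28 days". The personnel part of section 9 promises repeated device reminders from T1 onwards, without a frequency.

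**Arm-specific features.** Section 5.3 gives activity feedback to the intervention arm and sends partner-written messages on days when the goal is reached. Sections 3.1.2 and 5.6 (Study partner) let the partner see the accelerometer results. Section 3.8.3.c saves a weekly donation "if the participant achieves 100% of their goal on a given week". It names no arm, but 3.8.3.d limits the cross-over version to people entering the intervention. Sections 3.8.1 and 3.8.2 pay both arms the same $20 for completing accelerometry.

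**The concern.** Steps taken while the device is off are not counted. A day with longer wear therefore scores more steps even if behaviour has not changed. If the intervention makes people wear the device longer, the step contrast mixes a behavioural effect with a measurement effect.

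Randomisation does not protect against this, because the wear difference arises after allocation. A larger sample does not help either, since it narrows the standard error around a biased difference. Without a written rule, partly worn days would have to be dealt with after the data are in hand.

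**Working it through.** **1. The plan's own figure.** The SAP gives a difference of 10.0%, SD 14.0%, 80% power and two-sided alpha 0.05. Per arm, n = 2 × [14 × (1.960 + 0.842) / 10]² = 30.8, so 31 against the stated 30. Power at 30 per arm is 0.79. The figure reproduces. The SAP does not say which activity measure the percentages refer to.

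**2. Where wear could differ.**

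| Feature | Baseline week | Weeks 2 and 4, intervention | Weeks 2 and 4, control |
|---|---|---|---|
| Daily wear reminder | none described | yes, if sent to this arm | not stated |
| General device reminders | yes | yes | yes |
| Activity feedback | none described | yes | none described |
| Goal-dependent partner messages; partner sees data | no | yes | no partner in period 1 |
| Goal-dependent donation | no | implied | implied not |
| $20 for accelerometry | same in both arms | same | same |

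**3. What survives the planned contrast.** The model tests group × time. Let every participant gain s hours of wear from baseline to follow-up, and let the intervention arm gain d hours more. The contrast carries (s + d) − s = d. A reminder sent to both arms feeds s and largely cancels. Only d matters, and the feedback, messages and partner visibility are the features that could produce it.

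**4. Effect on steps.** Assumptions, none from the documents: baseline waking wear H of 13 to 15 h/day, a constant step rate over waking hours, and no true effect. Spurious gain = d / H.
- d = 0.5 h/day: 0.5/15 = 3.3% to 0.5/13 = 3.8%.
- d = 1 h/day: 1/15 = 6.7% to 1/13 = 7.7%.
- d that would equal a 10% difference: 0.10 × 13 h = 78 min to 0.10 × 15 h = 90 min per day.

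**5. Illustration for the test.** This adds the assumption that the SAP's 14% SD applies to percentage change in steps. At 30 per arm, SE = 14 × √(2/30) = 3.61. With bias b, the two-sided rejection rate is Φ(b/SE − 1.96) + Φ(−b/SE − 1.96).
- d = 0.5 h/day: 15 to 19%.
- d = 1 h/day: 45 to 57%.
- At 60 per arm (the protocol's 120 participants), SE = 14 × √(2/60) = 2.56, and d = 0.5 h/day gives 26 to 33%.

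**6. Effect on sedentary time.** The Introduction cites 9.6 sedentary hours per day in adults. Over an assumed 15 to 17 waking hours that is a fraction of 9.6/15 = 0.64 to 9.6/17 = 0.56. If non-wear is excluded, each extra hour of wear adds about 60 × 0.64 = 38 to 60 × 0.56 = 34 sedentary minutes. In the min/day form, longer wear would thus tend to count against the intervention. In the percentage form, numerator and denominator grow together and the effect is small.

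**The case against.** A reader might infer that both primary outcomes are raw daily totals, that participants are reminded only in follow-up weeks, that everything rewarding wear goes to the intervention arm, and that longer wear therefore always looks like more activity. The documents do not support that reading:
- The analysis text in 6b uses a percentage for sedentary time, which is largely robust to wear. In minutes, the bias would probably run the other way.
- Section 5.3 names no arm for the weeks 2 and 4 reminders, and the Figure 2 caption speaks of each participant. If both arms receive them, their effect largely cancels. Section 9 also promises reminders throughout.
- The payment tied most directly to wear, the $20, is equal across arms. The donation is at most $3 a week, and limiting it to one arm in period 1 is an inference from 3.8.3.d.
- The documents do not say how goal attainment is verified. Donation goals cover all four weeks, while section 5.5 records accelerometry in two of them.
- Round-the-clock wear, wear screening and make-up days are planned, and nothing in the documents shows that a gap of an hour a day is likely.

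All of this stands, and it narrows the point to steps. It does not remove it. Equal payment does not offset unequal feedback and partner visibility. Screening identifies non-wear but does not say how a partly worn day enters the daily average. The make-up days are worded for the intervention period, so they may not cover the baseline week.

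**Conclusion.** The concern holds for one primary outcome. Steps per day has no wear denominator or adjustment, and several intervention-arm features give that arm an added reason to keep the device on. The unequal description of daily reminders across weeks is a secondary weakness, and it becomes a between-arm bias only if the arms are prompted differently. The sedentary outcome is exposed only in its min/day form, and its two definitions in 6b need reconciling.

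The size is hypothetical: about 3 to 8% spurious step difference for a 0.5 to 1 h/day wear differential, given 13 to 15 h of baseline waking wear and a constant step rate. If the recovered hours are quieter than average the bias is smaller, and if they include walks it is larger. Any comparison with the SAP's 10.0% is indicative only. The documents support the possibility of bias, not a claim that wear will differ. The change is worth making because it is cheap and protects a primary outcome.

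**What to change.** - **Sections 5.3 and 5.5:** send one identical daily wear reminder, separate from the intervention message, to both arms in the baseline week, week 2 and week 4. Offer make-up wear days on the same terms in all three weeks.
- **Section 6b and SAP:** compute steps per day over valid days under one prespecified rule on waking hours per day and days per week, with the thresholds fixed before the data are seen. Define the sedentary primary outcome once, as a percentage of valid wear time, in both the table and the analysis text.
- **Reporting:** tabulate waking wear time by arm and week. Wear is itself a post-randomisation variable, so readers need to see whether the valid-day rule removes different amounts of data from each arm.
- **Sensitivity analysis:** repeat the step analysis as steps per waking wear hour. At a constant step rate this removes the bias shown above. A valid-day rule alone does not, because wear can still differ among valid days.

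The cost is an extra automated reminder in the baseline week (and for controls, if they do not already receive one), plus a few sentences in the protocol and SAP. A few low-wear weeks will become missing or need make-up days.
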